# 2.2 Objectives

### 2.2.1 Primary

1) The primary objective of this protocol is to evaluate the safety of FCX-007.

### 2.2.2 Secondary

- 1) To evaluate mechanism of action of FCX-007 at visits 5 (Week 4), 6 (Week 12), 8 (Week 25), 10 (Week 52), and unscheduled visits through the evaluation of skin biopsies for C7 expression and the presence of anchoring fibrils.
- 2) To evaluate the efficacy of FCX-007 through an intra-subject paired analysis of target wound area at visits 5 (Week 4), 6 (Week 12), 8 (Week 25), 10 (Week 52), and unscheduled visits, comparing FCX-007 treated wounds to untreated wounds through investigator assessment of wound healing based on the digital images of wounds.

[figure not shown]
CONFIDENTIAL Page 16 of 75

# 3 Experimental Plan

### 3.1 Study Design

This is a Phase I/II Study of FCX-007 (Genetically-Modified Autologous Human Dermal Fibroblasts) for Recessive Dystrophic Epidermolysis Bullosa (RDEB) being conducted by Fibrocell to evaluate FCX-007 in subjects with RDEB. Up to twelve subjects will be enrolled, up to six (6) in Phase I, and up to six (6) in Phase II. Phase I will enroll adult subjects only; Phase II can enroll adults and pediatric subjects (aged seven (7) or older). Within Phase I, subjects will be assigned to one of two arms: subjects with NC1+ status will be enrolled into Arm A and subjects with NC1- status will be enrolled into Arm B. The arms will enroll independently. In Phase I, the study may enroll an equivalent number of subjects to Arm A and Arm B (n=3 each arm). In Phase II, the study will target enrolling 3 subjects to each arm, but will allow a disproportionate distribution of subjects between Arm A and Arm B to equal 6 total subjects.

Figure 2 - High-Level Study Design

One administration of FCX-007 will consist of up to sixty (60) 0.25 mL intradermal injections in wounded and/or intact skin. The majority of the injections will be administered around the margin of target wounds and at least 6 injections will be administered to intact skin. The Investigator will attempt to administer all 15mL of FCX-007. This will be accomplished by selecting target wounds that are as close as possible to 54 linear cm, leaving at least 6 administrations for intact skin, for a total of 60 injections.

For the wound administrations, subjects will receive FCX-007 administered intradermally to one, two or three paired target wounds at Visit 3 (Day 0). Subjects will receive a second administration to wounded and/or intact skin at Visit 5 (Week 4).

In this study, one wound in each target wound pair will be used as a control for efficacy and safety evaluations. FCX-007 administered wounds will be compared within paired target wounds to untreated wounds.

CONFIDENTIAL Page 17 of 75

Final Version 8.0, 29 Oct 2019

As there is no previous human experience with FCX-007, treatment administration will be staggered in two places:

- 1. Between the first and second enrolled subjects in each arm.
- 2. Between the third and fourth enrolled subjects in each arm.

Proceeding to administration of FCX-007 after a stagger requires that the previous subject complete Week 4 evaluations and the Investigator must have received approval from the Data Safety Monitoring Board (DSMB) to continue the study prior to the next subject's FCX-007 administration.

At a minimum, FDA and DSMB approvals are required for enrollment of pediatric subjects. Local oversight committees may also require approval.

Each phase of the study is divided into four (4) periods: Screening, Wound Monitoring, Treatment, and Long-Term Follow-Up. The Screening Period consists of entry criteria evaluations, the collection of one set of three 3-4 mm biopsies for FCX-007 manufacturing, and the identification and photography of potential target wounds. FCX-007 manufacturing requires about 4 months. This period is the Wound Monitoring Period. Subject target wounds may be imaged a minimum of two times (at least 4 weeks apart) during this period. The purpose of the imaging is to identify wounds with the most consistent wound areas that meet criteria, and to establish a baseline area that takes into account natural wound area variation. The Wound Monitoring Period is expected to have a duration of approximately four months; however, this period can extend beyond four months to accommodate patient scheduling, variations in manufacturing duration and protocol mandated delays (i.e. pauses due to staggered treatment).

After FCX-007 manufacturing is complete, Fibrocell (the Sponsor) and the Investigator will mutually agree on the date of receipt of FCX-007. The duration of the Treatment Period may fluctuate between two and four days. The Treatment Period visits (Day -2 to Day 2) will be scheduled so that the day of dosing (Day 0) is the day of receipt of FCX-007. Prior to dosing, wounds are identified that meet treatment criteria based on imaging results obtained. Up to three pairs of target wounds may be identified for each subject and the Investigator will pair the target wounds according to similarity in wound area.

One wound in each pair will receive FCX-007 and the other wound no treatment.

Safety and proof of mechanism evaluations are conducted during site visits at Visits 5, 6, 8 and 10 (weeks 4, 12, 25, 52), and unscheduled visits. Proof of mechanism will be monitored through assays conducted on biopsies taken from target wounds and areas of intact skin in which FCX-007 was administered.

Safety is monitored throughout the study, captured during on-site visits and while the subject is off-site through adverse event diaries. The following assessments in each subject will be assessed: adverse events (AEs), physical examinations, vital signs, clinical laboratory evaluations (including C7 antibodies, and RCL), medical history, and prior/concomitant medications, as appropriate. A DSMB will periodically review subject safety data.

CONFIDENTIAL Page 18 of 75

RDEB Phase I/II Protocol

Final Version 8.0, 29 Oct 2019

The Long-Term Follow-Up is a 15-year period following Week 52/ET in which safety is monitored (including RCL testing yearly and any new malignancies to 15-years) at a minimum annually. If all post-treatment RCL assays are negative during the first year (e.g., Weeks 4, 12, 16, 25, 32, and 52), collection of the yearly follow-up samples will be discontinued.

### 3.2 Number of Investigative Sites

One (1) to three (3) investigative sites will participate in the study.

# 3.3 Number and Source of Subjects

The enrollment target is up to twelve (12) subjects: Up to six subjects in Phase I and up to six (6) subjects in Phase II. A seventh subject may be enrolled into Phase II at the discretion of the sponsor.

In Phase I, 3 NC1+ subjects may be enrolled to Arm A and 3 NC1- subjects may be enrolled to Arm B. In Phase II, the study will target enrolling 3 subjects to each arm, but will allow a disproportionate distribution of subjects between Arm A and Arm B to equal 6 total subjects. All potential subjects must be properly consented, meet all inclusion/exclusion criteria, and undergo all screening procedures to be eligible for participation in this study.

# 3.4 Estimated Study Duration

The duration is about 20 months per subject, including the Screening, Wound Monitoring and Treatment Periods. Recruitment is anticipated to take approximately 8 months, resulting in total study duration of approximately 28 months. The end of Treatment Period Visit is scheduled to occur at the end of the 12-month treatment phase. Safety data will continue to be collected by clinic visit or telephone contact approximately every 1 year for at least 15 years after the treatment phase.

CONFIDENTIAL Page 19 of 75

Final Version 8.0, 29 Oct 2019

# 4 Subject Eligibility

Investigators will be expected to maintain a screening log of all potential study candidates that includes limited information about the potential candidate (e.g. gender, age, race) and outcome of the screening process (e.g. enrolled into study, reason for ineligibility, or refused to participate).

### 4.1 Inclusion Criteria

To be eligible for inclusion, each subject must fulfill each of the following criteria:

- 1. Age
  - a. Phase I: Eighteen (18) years old or older.
  - b. Phase II: Seven (7) and older.
- 2. Diagnosis of recessive dystrophic epidermolysis bullosa (RDEB) (inclusive) by:
  - a. Clinical diagnosis
  - b. Immunofluorescence (IF) evaluation
  - c. Electron microscopy (EM/IEM) evaluation
  - d. Confirmation of RDEB C7 mutations in the subject
- NC1 Status
  - a. Arm A: Positive for the NC1 domain of C7 (NC1+) as determined by genetic testing results showing one or no loss of function mutations in exons 1-28.
  - Arm B: Negative for the NC1 domain of C7 (NC1-) as determined by genetic testing results showing two loss of function mutations in exons 1-28.
- 4. NC2 Status: negative or weakly positive for LH24 antibody staining as determined by immunoelectron microscopy (IEM).
- 5. Subjects and guardians, who are, in the opinion of the Investigator, able to understand the study, co-operate with the study procedures and are willing to return to the clinic for all the required follow-up visits.

CONFIDENTIAL Page 20 of 75

Final Version 8.0, 29 Oct 2019

### 4.2 Exclusion Criteria

Subjects will be excluded from the study if any of the following criteria are met:

- 1. Medical instability limiting ability to travel to the investigative center.
- 2. Active infection with HIV, hepatitis B or hepatitis C, as determined by hepatitis B surface antigen screening, detection of hepatitis C antibodies, or positive result of hepatitis C PCR analysis.
- 3. The presence of antibodies to the basement membrane of monkey esophagus by indirect immunofluorescence using the subject's serum.
- Evidence of systemic infection.
- 5. Current evidence of metastatic squamous cell carcinoma at the site to be injected.
- 6. Known allergy to any of the constituents of the product.
- 7. Active drug or alcohol addiction.
- 8. Hypersensitivity to anesthesia chosen (lidocaine/prilocaine cream, moderate sedation, or general anesthesia).
- 9. Receipt of a chemical or biological study product for the specific treatment of RDEB in the past six months
- 10. Women who are pregnant or breast-feeding.
- 11. Any clinically significant abnormal laboratory result from Day -2 (Grade 2 or higher on the National Cancer Institute [NCI] toxicity scale), except for the following:
  - a. Albumin < 2.5 g/dL,
  - b. Leukocytes > 20K/uL,
  - c. Hemoglobin < 7.5 g/dL
- 12. Clinically significant abnormalities (Grade 2 or higher on the NCI toxicity scale) identified through medical history and physical examination at Day 0, with the following exceptions:
  - a. Anorexia, can enroll up to Grade 4 (inclusive)
  - b. Constipation, can enroll up to Grade 2 (inclusive)
  - c. Dysphagia, can enroll up to Grade 4 (inclusive)
  - d. Keratitis, can enroll up to Grade 4 (inclusive)
  - e. Bone pain, can enroll up to Grade 2 (inclusive)

CONFIDENTIAL Page 21 of 75

Final Version 8.0, 29 Oct 2019

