#### **Exclusion Criteria**

- 1. Medical instability limiting ability to travel to the investigative center.
- 2. Active infection with HIV, hepatitis B or hepatitis C, as determined by hepatitis B surface antigen screening, detection of hepatitis C antibodies, or positive result of hepatitis C PCR analysis.
- 3. The presence of antibodies to the basement membrane of monkey esophagus by indirect immunofluorescence using the subject's serum.
- 4. Evidence of systemic infection.
- Current evidence of metastatic squamous cell carcinoma at the site to be injected.
- 6. Known allergy to any of the constituents of the product.
- 7. Active drug or alcohol addiction.
- 8. Hypersensitivity to anesthesia chosen (lidocaine/prilocaine cream, moderate sedation, general anesthesia).
- 9. Receipt of a chemical or biological study product for the specific treatment of RDEB in the past six months
- 10. Women who are pregnant or breast-feeding.
- 11. Any clinically significant abnormal laboratory result from Day -2 (Grade 2 or higher on the National Cancer Institute [NCI] toxicity scale), except for the following:
  - a. Albumin < 2.5 g/dL,
  - b. Leukocytes > 20K/uL,
  - c. Hemoglobin < 7.5 g/dL
- 12. Clinically significant abnormalities (Grade 2 or higher on the NCI toxicity scale) identified through medical history and physical examination at Day 0, with the following exceptions:

CONFIDENTIAL Page 10 of 75

Fibrocell	Techno	logies

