Persistent blistering begins at birth and contributes to the high mortality risk due to bacterial infection. In a study of 41 RDEB patients, the infectious causes of pneumonia and sepsis resulted in death in 14.6% and 9.8% respectively (Fine, 2010). Patients who survive bacterial sepsis during early infancy are at a high risk of later developing more severe complications such as growth retardation due to gastrointestinal involvement (Fine, 2008), multifactorial anemia, esophageal strictures, corneal scarring and/or progressive blindness (Fine, 2004), post streptococcal glomerulonephritis, renal failure, progressive hand and foot deformities such as pseudosyndactyly (Fine, 2005), muscle contractures that restrict movement, anemia, esophageal strictures (Fine, 2008), microstomia, obliteration of the oral vestibule, dysphagia, rapid tooth decay, nail deformities, and hair loss. In addition, patients with the severe generalized subtype have an increased lifetime risk (over 90%) (RAC, 2007) of developing aggressive squamous cell

CONFIDENTIAL Page 12 of 75

Final Version 8.0, 29 Oct 2019

carcinoma. 87% die by the age of 45 due to metastatic squamous cell carcinoma (Fine, 2010).

Currently there is no effective therapy for this disease. Nearly 10% of RDEB patients die before the age of 10, almost 40% by the age of 20, and 72% before the age of 30. Death is usually the result of aggressive squamous cell carcinoma, sepsis, or of malnutrition due to an inability or unwillingness to eat due to mouth or esophagus involvement (RAC, 2007).

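### Exclusion criterion 11, read literally, exempts the most extreme albumin, leukocyte and hemoglobin values, when the listed figures were probably meant as exclusion limits

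*Combined protocol and SAP*

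**What the plan says.** Criterion 11 in section 4.2 applies to clinically significant abnormal laboratory results from Day -2. It excludes those that are "Grade 2 or higher on the National Cancer Institute [NCI] toxicity scale), except for the following". Three items follow: "Albumin < 2.5 g/dL", "Leukocytes > 20K/uL" and "Hemoglobin < 7.5 g/dL". The synopsis carries the same list with the same inequality signs.

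Criterion 12 applies a Grade 2 rule to abnormalities "identified through medical history and physical examination at Day 0", with its own exceptions for anorexia, constipation, dysphagia, keratitis and bone pain.

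The Schedule of Events (Table 2) places hematology and chemistry at Visit 1, at Visit 2 (Day -2), and then not again until Week 4. Section 1.1 names among the complications of the disease "multifactorial anemia, esophageal strictures, corneal scarring and/or progressive blindness" and, as a cause of death, "malnutrition due to an inability or unwillingness to eat due to mouth or esophagus involvement". The document does not reproduce the NCI grade limits for any analyte.

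**The concern.** The items after the word *except* are the ones the exclusion does not reach. All three inequalities point toward the sicker side: low albumin, high leukocytes, low hemoglobin. A site that follows the sentence as it stands would therefore not use criterion 11 to keep out a subject with very severe anemia, very low albumin or a very high leukocyte count.

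The primary objective is safety, and these are the only numeric laboratory values in the eligibility criteria. Treated subjects undergo up to 60 intradermal injections per administration, repeated biopsies, and blood draws of about 19 mL at follow-up visits. Anesthesia may extend to moderate sedation or general anesthesia (Appendix A). Phase II may include children from age 7.

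Misreading could also do harm in the other direction. Day -2 falls after roughly 120 days of autologous manufacturing (section 6.1.1), so a subject wrongly excluded then loses product already made. With one to three sites (section 3.2), the same line could be applied in opposite ways.

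**Working it through.** The plan gives no figure to reproduce here; the check is a logical reading of the criterion.

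**Inputs.** From section 4.2 and the synopsis: the Grade 2 rule and the cut-offs of 2.5 g/dL (albumin), 20K/uL (leukocytes) and 7.5 g/dL (hemoglobin). Not in the documents: G, the value at which NCI Grade 2 begins for each analyte.

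**Step 1. Literal rule**, each analyte taken separately:

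excluded = (clinically significant) AND (Grade 2 or higher) AND NOT (beyond the cut-off)

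For any value beyond the cut-off the last term is false, so the whole expression is false whatever G is. Hemoglobin of 7.4, 5 or 3 g/dL, albumin of 2.4 or 1.0 g/dL, and leukocytes of 21K or 100K/uL are all outside the reach of criterion 11.

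**Step 2. Probable intended rule:**

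excluded = (clinically significant) AND (beyond the cut-off)

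Here the same example values are excluded if judged clinically significant. For values beyond the cut-offs, the two rules give opposite answers.

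**Step 3. What the literal rule does to milder values.** This depends on G. The values of G below are assumptions chosen to fall on either side of each cut-off; they are not NCI limits.

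| Analyte | Assumed G | Literal rule, milder side of the cut-off | Literal rule, beyond the cut-off |
|---|---|---|---|
| Hemoglobin | 9.0 | significant values from 7.5 to 9.0 excluded | below 7.5 not excluded |
| Hemoglobin | 7.0 | none excluded | below 7.5 not excluded |
| Albumin | 3.0 | significant values from 2.5 to 3.0 excluded | below 2.5 not excluded |
| Albumin | 2.0 | none excluded | below 2.5 not excluded |
| Leukocytes (high) | 15K | significant values from 15K to 20K excluded | above 20K not excluded |
| Leukocytes (high) | 25K | none excluded | above 20K not excluded |

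The last column does not change with G; the third column does.

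**Step 4. Is there a limit elsewhere?**

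- Exclusion 1 covers medical instability only as it limits travel; exclusion 4 covers systemic infection.
- Criterion 12 has no exemption for anemia, low albumin or leukocytosis, and medical history includes hematological disease (sections 7.1.3 and 11.2). A known severe anemia could be caught there, but criterion 12 works through history and examination, not through the Day -2 result.
- Section 11.6.1 asks for abnormal results that are unexpected or unexplained to be repeated.
- Section 5.3 lets the investigator or sponsor withdraw a subject for safety. Section 11.1.1 lets the Medical Monitor interrupt entry or dosing.
- Eligibility is rechecked at Visits 2 and 3 (sections 7.3.1 and 7.3.2), but against the same wording.

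None of these states a numeric limit for the three analytes.

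**Step 5. Reach.** Up to 12 subjects, and section 3.3 allows one more in Phase II: 12 + 1 = 13. The documents do not say how many might have such values.

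**The case against.** The strongest reply is that an ordinary reader would take the three items as the analytes' own cut-offs. They stand in a list of reasons to exclude, and their inequalities point the way exclusion limits normally point. On that reading all three limits exist and the trial is run sensibly. This stands as the likeliest account of intent. It does not rescue the sentence, which says the opposite.

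A second reply is that a wide waiver was deliberate, because anemia and malnutrition belong to the disease. The documents do not rule this out, but nothing in them says that albumin, hemoglobin and leukocytes were to be left without any limit.

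A third is that the backstops make it improbable that a subject with, say, a hemoglobin of 3 g/dL would be dosed. That also stands, and it is why the matter is minor.

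Two stronger readings are tempting and should be resisted. A reader might infer that the criterion is inverted by severity, turning away milder cases while admitting worse ones. The documents cannot show this, because it depends on NCI limits they do not give. A reader might also point to criterion 12, where every exception carries a maximum grade, as proof that bounds were forgotten in criterion 11. That contrast is weak. Three of the five maxima are Grade 4, which on the adverse-event scale in section 13.2 is immediately life-threatening, with only the fatal grade above it. If eligibility grades follow that scale, those three bounds restrict almost nothing.

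**Conclusion.** Wrong as written; minor severity. Followed literally, criterion 11 excludes no albumin below 2.5 g/dL, no leukocyte count above 20K/uL and no hemoglobin below 7.5 g/dL. This conclusion rests only on the wording, which is identical in both places, and needs no assumption about NCI grades. That the figures were meant as relaxed exclusion limits is a judgment about intent, probable but not stated.

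The documents do not support saying that severely abnormal subjects would enter unchecked: several safeguards remain, though without a laboratory limit. The effect is confined to eligibility of at most 12 or 13 subjects. No endpoint, analysis or error rate changes.

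**What to change.** In both the synopsis and section 4.2, replace the exceptions to criterion 11 with one sentence:

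> except that subjects with Grade 2 or higher albumin, leukocyte (elevated) or hemoglobin results can enroll provided albumin >= 2.5 g/dL, leukocytes <= 20K/uL and hemoglobin >= 7.5 g/dL.

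Low leukocyte counts stay under the general Grade 2 rule.

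The drafting cost is three short items in two places. The substantive cost is that a few subjects with extreme values who pass the literal text would be excluded, possibly including some the sponsor meant to admit. In return, subjects with milder Grade 2 or higher values that the literal text may shut out could enroll, and all sites would apply the same rule.

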# 5 Subject Enrollment and Withdrawal

Written protocol and informed consent approval are required from the IRB prior to enrollment. Assent form approval is required from the IRB prior to enrolling subjects below the age of consent. All subjects or their respective legal guardians must personally sign and date the relevant consent and/or assent form before enrollment.

# 5.1 Subject Identification and Number Assignment

Subjects who sign the informed consent form will be assigned a 4-digit subject identification number. Subject identification numbers will begin with "XX" = pre-defined site number, and end with "XX" = subject number (sequential, starting with 01). This number will identify the subject throughout the study and must be used on all study documentation related to that subject.

# 5.2 Concomitant Therapy and Skin Care

There are no restrictions on concomitant therapies and skin care. Throughout the study, any concomitant medications or treatments deemed necessary to provide adequate supportive care may be prescribed. In particular, medication should be considered during and after the injections to treat pain and/or anxiety (i.e. lorazepam). Routine skin care for RDEB patients will continue throughout the study.

# 5.3 Withdrawal of Subjects

A subject is free to withdraw from the study at any time for any reason without prejudice to their future medical care by the physician or at the institution. The Investigator or Sponsor may also withdraw the subject at any time in the interest of subject safety or for other reasons. Criteria for withdrawal include:

- 1. Consent/assent is withdrawn
- 2. The subject refuses treatment and/or procedures/observations.
- 3. Occurrence of unmanageable adverse events, or pregnancy.
- 4. For other reasons (e.g., significant protocol violation, non-compliance).
- 5. The Sponsor may be contacted if clarification is required.

The primary reason for withdrawal must be recorded on the CRF. Comments or complaints made by the subject must also be recorded on the CRF. Withdrawal information will be communicated to the DSMB at each meeting. Withdrawal should be discussed with the medical monitor prior to withdrawal when possible. Subjects who wish to discontinue treatment or study procedures after receipt of FCX-007 will be asked to continue in the Long-Term Follow-Up Period (Section **7.5**). Subjects who withdraw prior to FCX-007 administration will be considered a screen failure and will be replaced. The Sponsor reserves the right to terminate the study.

CONFIDENTIAL Page 22 of 75

[figure not shown]
Final Version 8.0, 29 Oct 2019

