## 7.5 Long-Term Follow-Up Period

Upon completion of the End of Study / Early Termination Visit, subjects will enter into the Long-Term Follow-Up Period.

#### 7.5.1 Years 1 - 5

At a minimum, subjects will be contacted yearly for at least 5 years. Subjects will be contacted by phone. In addition, the subject's primary care provider will be asked to contact the Investigator regarding any unexpected or serious adverse events. Telephone contact reports will document the discussions and the information obtained will be captured on case report forms. The following activities will occur at the one-year follow-up intervals:

- Collection and analysis of blood sample for RCL testing (can be done remotely).
  - If all post-treatment assays are negative during the first year (e.g., Weeks 4, 12, 16, 25, 32, and 52), collection of the yearly follow-up samples will be discontinued.
- Recording of exposures to mutagenic agents and other medicinal products
- Recording of any new serious adverse events, hospitalizations, or illnesses (including new malignancies, new incidence or exacerbation of a pre-existing neurologic disorder, new incidence or exacerbation of a prior rheumatologic or other autoimmune disorder, new incidence of a hematologic disorder).
- Discussion with primary care provider regarding medication and medical history.
- If a skin cancer occurs in the region of the FCX-007 administration, attempts will be made to collect samples of the skin cancer to evaluate cells for the presence of viral vector.

#### 7.5.2 Years 6 - 15

Subjects will continue to be followed-up on an annual basis for at least 15 years following FCX-007 administration. Follow-ups from years 6 to 15 include:

- Collection and analysis of blood sample for RCL testing (can be done remotely).
  - If all post-treatment assays are negative during the first year (e.g., Weeks 4, 12, 16, 25, 32, and 52), collection of the yearly follow-up samples will be discontinued.

CONFIDENTIAL Page 37 of 75

FI-EB-001 RDEB Phase I/II Protocol

Final Version 8.0, 29 Oct 2019

- Recording of exposures to mutagenic agents and other medicinal products
- Recording of any new adverse events, hospitalizations, or illnesses (including new malignancies, new incidence or exacerbation of a pre-existing neurologic disorder, new incidence or exacerbation of a prior rheumatologic or other autoimmune disorder, new incidence of a hematologic disorder).

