#### A: Treatment of an Entire Wound

#### **B: Treatment of a Partial Wound**

#### 9.4.3 Visit 5 Administration

Target wounds are administered investigational product up to two times throughout the treatment period; once at Visit 3 (Day 0) and again at Visit 5 (Week 4).

CONFIDENTIAL Page 45 of 75

Final Version 8.0, 29 Oct 2019

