For subject safety, investigators should continue to follow patients in accordance with study visits and procedures as outlined in the protocol. An occurrence of any of these safety observations will be shared with all study Investigators, DSMB and the appropriate authorities. The DSMB will review the results of the safety investigation and may request any additional data needed to assess the safety of restarting product administration. The DSMB will determine if the suspension can be lifted or if the trial will need to terminate based on their review of the safety investigation.

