## 14.9 Handling of Missing and Incomplete Data

Missing values will be captured as such in the CRF database. No imputation for missing data is planned for efficacy analyses, although different assumptions depending on the analysis, may be explored. Standard clinical monitoring and data management practices will be used to ensure the integrity of data.

CONFIDENTIAL Page 63 of 75

Fibrocell Technologies RDEB Phase I/II Protocol Final Version 8.0, 29 Oct 2019

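### Section 5.3 gives a dosed subject who declines only the Week 4 administration no stated route to stay on the Week 12, 25 and 52 visits, so those scheduled paired-wound and C7 antibody data may be lost

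*Combined protocol and SAP*

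**What the plan says.** Section 5.3 lists, as one withdrawal criterion, "The subject refuses treatment and/or procedures/observations". Refusing product and refusing observation share that line. For subjects already dosed it then says: "Subjects who wish to discontinue treatment or study procedures after receipt of FCX-007 will be asked to continue in the Long-Term Follow-Up Period". Withdrawal by others is discretionary: "The Investigator or Sponsor may also withdraw the subject at any time in the interest of subject safety or for other reasons".

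Section 7.5 sets the entry point to that period: "Upon completion of the End of Study / Early Termination Visit, subjects will enter into the Long-Term Follow-Up Period". For Years 1 to 5 it adds: "Subjects will be contacted by phone". The follow-up column of Table 2 is marked only for adverse events and RCL.

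Two other sections bear on subjects who receive fewer than two administrations. Section 9.4.3 says "Target wounds are administered investigational product up to two times throughout the treatment period". Section 11.1.1, on a safety-triggered suspension of dosing, says "investigators should continue to follow patients in accordance with study visits and procedures as outlined in the protocol".

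On analysis, Section 14.9 says "No imputation for missing data is planned for efficacy analyses", while allowing different assumptions to be explored. The opening of Section 14 defines a treatment endpoint to deal with incomplete data and early terminations.

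**The concern.** Both wounds of a pair can still be imaged and assessed after a missed second administration, and the Day 0 random assignment within the pair still stands. Nothing in the design requires observation to stop when product stops. Yet Section 5.3 names one destination for a dosed subject who stops treatment, and that destination collects none of the wound or C7 antibody data.

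At stake are the later time points of the paired-wound secondary objective, which would show whether any effect lasts, and scheduled antibody sampling, which serves the primary safety objective. With no imputation planned, by-visit results after Week 4 would come only from subjects who stayed on schedule. If willingness to accept the second round is related to how the wound or the subject responded, that group is selected. With at most 12 subjects planned (plus an optional seventh in Phase II), one case matters.

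**Working it through.** The plan has no figure to reproduce: Section 14.1 states that no formal sample size calculation was done. The check compares the sections and counts time points.

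**1. Follow a subject who is dosed on Day 0, declines the Week 4 administration and is willing to keep attending.**

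| Step | Section | What is collected |
|---|---|---|
| Visit 5 (Week 4) | 7.3.4 | Imaging, wound assessment, C7 antibody, RCL |
| Stops treatment | 5.3 | Asked to continue in Long-Term Follow-Up; no alternative stated |
| Before entering follow-up | 7.3.9, 7.5 | One Early Termination visit with the Visit 10 procedures: imaging, wound assessment, C7 antibody, RCL, biopsies |
| Long-Term Follow-Up | 7.5, Table 2 | At least yearly contact, adverse events and RCL; no imaging, wound assessment or C7 antibody assay |

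**2. Count the scheduled time points lost.**

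- Paired-wound objective (Section 2.2.2): Weeks 4, 12, 25 and 52. Week 4 is kept; Weeks 12, 25 and 52 are lost: 3 of 4.
- C7 antibody after dosing (Section 11.6.4): fixed at Weeks 4, 12, 25 and 52, so again 3 of 4. If Visits 7 and 9 are held in the office, Weeks 16 and 32 are added and the loss is 5 of 6.
- Returned in exchange: one Early Termination set. Its timing is not fixed. Held soon after Week 4, it would add little about Weeks 12 to 52.

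**3. Check whether the analysis plan recovers the loss.** The treatment endpoint of Section 14 is carried into the C7 expression analysis (14.6.1). The target wound analyses (14.6.3) are by post-treatment visit and do not use it. FAS membership (14.4.2) needs only one paired post-administration assessment, so the subject stays in the population but contributes nothing scheduled at Weeks 12 to 52.

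**4. Compare with suspended dosing.** Under Section 11.1.1, a subject with one administration whose second is held back by a suspension stays on visits and procedures. Under Section 5.3, a subject with the same exposure who declined the second is pointed to Long-Term Follow-Up.

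**5. Scale.** One subject is 1/12 = 8.3% of the trial or 1/6 = 16.7% of a six-subject phase.

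The chance of at least one such subject is 1 − (1 − d)^N, where d is the refusal rate. The documents give no d, so these rates are assumptions:

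| d | N = 6 | N = 12 |
|---|---|---|
| 5% | 0.27 | 0.46 |
| 10% | 0.47 | 0.72 |
| 20% | 0.74 | 0.93 |

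For illustration only, assume one wound pair per subject and an exact sign or signed-rank test (the plan names no test). The smallest attainable two-sided p is 2 × (1/2)^n: 0.031 for n = 6 and 0.0625 for n = 5. One loss from a six-subject phase would then put 0.05 out of reach at that visit. If the optional seventh Phase II subject is enrolled, one loss leaves n = 6 and 0.031.

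**The case against.** The strongest reply is that Section 5.3 permits and requests; it does not compel. The investigator or sponsor may withdraw a subject, and the subject will be asked to continue in follow-up. Everyone enters Long-Term Follow-Up eventually, so the sentence can be read as a minimum request for safety retention. Section 9.4.3 already contemplates fewer than two administrations. This stands to the extent that loss is not certain. It does not supply a route to stay on schedule: a site following the text has only one destination to offer.

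A reader might infer three stronger things that the documents do not support:

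- *That anyone declining the Week 4 dose loses all paired and antibody data.* Week 4 and one Early Termination set are kept, and unscheduled visits (Section 7.4) may add more.
- *That refusing one biopsy removes a subject from imaging.* Section 10.1 leaves the number and type of biopsies to the investigator and sponsor, and a Table 2 footnote lets the number vary.
- *That all antibody follow-up ends in subjects who reacted.* A positive C7 antibody result must be recorded as an adverse event (11.6.4). Adverse events are followed to an outcome where possible, with tests as appropriate (13.1.1), and medically significant related events until resolved or stable (13.2). What ends is scheduled sampling.

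It is also fair that Section 11.1.1 covers a different situation, a suspension in which the subject has refused nothing. The two sections do not strictly contradict each other. The comparison shows that the protocol already regards continued visits without further product as workable.

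Finally, testing is exploratory and the primary objective is safety. That limits the consequence for inference. It does not remove the case for keeping safety observation in a first-in-human product.

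**Conclusion.** The point holds in limited form. Section 5.3 merges stopping product with stopping observation and gives a willing subject who declines only the Week 4 administration no stated way to remain on the Week 12, 25 and 52 visits. If the section is followed as written, that subject loses 3 of 4 scheduled paired-wound time points and 3 of 4 fixed post-treatment antibody samples (5 of 6 if Visits 7 and 9 are in the office), less whatever one Early Termination visit provides.

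This rests on the subject attending the Visit 5 assessments and on the site following Section 5.3 literally. That the loss would be informative is plausible but not shown: the documents give neither refusal rates nor reasons. The percentages are one subject's share of the sample and do not estimate bias. The point is worth correcting because the remedy is cheap and the sample is small; it does not invalidate the design.

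**What to change.** Reconcile Sections 5.3, 7.3.9, 7.5, 9.4.3 and 11.1.1 on which assessments continue, along these lines:

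1. A subject who does not receive, or declines, a further administration but is willing to attend is asked to remain on the existing Table 2 assessments through Visit 10, for both wounds of each pair, C7 antibody and RCL.
2. The Early Termination visit followed by Long-Term Follow-Up is reserved for subjects who decline further visits.
3. Section 14.4 states that observations after a missed administration stay in the FAS under the wound's Day 0 assignment.

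This is about data collection. It proposes no dosing or clinical stopping rule, and attendance remains voluntary.

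The cost is a wording amendment to the withdrawal and follow-up text and one sentence in Section 14.4, with no visits, procedures or staff beyond Table 2. The small downside is that the FAS will include some single-dose wounds, which Sections 9.4.3 and 14.4.2 already allow.
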